5.3.1.3. Subgroup Analysis

Subgroup analyses of the efficacy endpoint of COVID-19 will be performed in select subgroups specified below based on the PP Set by treatment cohort. The efficacy endpoint of COVID-19 will be analysed by each of the subgroups using the same methods described for the primary analysis for each category of the following classification variables:

- Age groups: ≥ 18 and < 65 years, ≥ 65 years
- Stratification factor at randomization: ≥ 18 and < 65 years and not at risk, ≥ 18 and < 65 years at risk, ≥ 65 years
- Sex (female, male)
- Race
- Ethnicity
- Race and Ethnicity: non-Hispanic white, communities of color
- Each risk factor for severe COVID-19 illness as listed in Section 6.2.1 of the protocol

5.3.1.4. Variant-specific analysis of effectiveness

New SARS-CoV-2 variants have emerged. COVID-19 cases have been and will continue to be sequenced. Summary of variant cases by variants will be provided in adjudicated COVID-19 cases. Effectiveness of vaccine for specific variants will be assessed based on incidence rates if there are sufficient number of variants cases. In this variant-specific analysis, COVID-19 due to the specific variant will be considered as cases, and COVID-19 due to other variants will be censored at the time of documentation of COVID-19.

Analysis of effectiveness against variants may be performed if there are sufficient numbers of variants cases for Primary series, and for booster, respectively.

Number of variant cases, person-time, and incidence rate will be provided. Person-time will be calculated as the total time, for primary series, from dose 1 of primary series; for booster, from booster date, to the earliest of the date of COVID-19, censor, last date of

study participation, or efficacy data cutoff date, whichever was earlier. The incidence rate will be calculated as the number of participants with an event divided by the number of participants at risk and adjusted by person-time (total time at risk) in each treatment group. The 95% CI will be calculated using the exact method (Poisson distribution) and adjusted by person-time.

For primary series, relative effectiveness of recent vaccinated participants (Placebo-mRNA-1273) vs. early vaccinated participants (mRNA-1273) will be assessed using the reduction in incidence rate, calculated as 1- incidence rate ratio (IRR). The 95% CI will be provided for the reduction in IR using the exact method.

5.3.2. Analysis of Other Efficacy Endpoints

The efficacy endpoints included in this section will be evaluated for Part C using Part C PP Set, for the primary series using PP Set with appropriate analysis period.

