5.4. Per-Protocol Set

The Per-protocol Set consists of all participants in mITT who received planned doses of IP per schedule and have no major protocol deviations, as determined and documented by Sponsor prior to database lock (DBL) and unblinding, which impact critical or key study data. Participants will be analyzed according to the treatment group to which they were randomized. Participants who did not receive the second injection of IP within [21, 42] days after the first injection date will be excluded from the Per-Protocol Set.

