3.9. Blinding and Unblinding

Part A of this study is an observer-blind part. The investigator, study staff, study participants, site monitors, and Sponsor personnel (or its designees) were blinded to the IP administered until unblinding in Part B, with the certain exceptions specified in Section 6.2.8 of the protocol. Refer to SAP Version 2.0 for more details.

Part B and Part C of the study is open-label.

4. Analysis Populations

The following analysis sets have been defined in SAP Version 2.0. Refer to SAP Version 2.0 for details.

- Randomization Set
- Full Analysis Set (FAS)
- Modified Intent-to-Treat (mITT) Set
- Per-protocol (PP) Set
- Per-Protocol Random Subcohort for Immunogenicity (PPRSI)
- Safety Set
- Solicited Safety Set

The following analysis sets are defined in this SAP for Part C:

- Part C Safety Set
- Part C Per-Protocol Random Subcohort for Immunogenicity (Part C PPRS)
- Part C Per-Protocol Immunogenicity Subset (Part C PPIS)
- Part C Per-Protocol Immunogenicity Subset – Pre-booster SARS-CoV-2 negative (Part C PPIS-Neg)
- Part C Per-Protocol Set (Part C PPS)

The following analysis sets are defined in this SAP for Primary Series (for those randomized to mRNA-1273 in Part A and those crossover to mRNA-1273 in Part B):

- Per Protocol Primary Series Set (PP Primary Series)
- Primary Series Safety Set

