4.6. Per-Protocol (PP) Primary Series Set

The PP Primary Series Set consists of all participants in Per-Protocol Set who received two doses of mRNA-1273 primary series per schedule in Part A or Part B, with negative pre-Dose 1 SARS-CoV-2 status, and had no major protocol deviations that impact critical or key study data.

Participants who did not receive the treatment as randomized in Part A, did not receive 2 doses of the primary series of mRNA-1273, or did not receive Dose 2 of mRNA-1273 within [21, 42] days after Dose 1 of mRNA-1273 will be excluded from the PP Primary Series Set.

PP Primary Series Set will be used for the effectiveness analysis of the mRNA-1273 primary series. PP Primary Series Set will also be used to assess effectiveness of participants received booster dose and those who did not receive booster dose by pre-booster SARS-CoV-2 status.

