5.3.1.2.1. Effectiveness of the primary series

Effectiveness of the primary series of mRNA-1273 in those vaccinated participants, will be assessed in participants initially randomized to the mRNA-1273 group (mRNA-1273, vaccinated from July-December 2020, early vaccinated) and those initially randomized to the placebo group (Placebo-mRNA-1273, vaccinated December 2020-April 2021, recent vaccinated) using the PP Primary Series Set. Part A and Part B data after Dose 1 of mRNA-1273 will be included for this analysis, and date of Dose 1 of mRNA-1273 will be used as the reference. The analysis period will be from Dose 1 of mRNA-1273 to earlier of last study participation, booster date, or data cutoff date for efficacy as presented in Table 1.

Using PP Primary Series Set, participants at risk will be those who did not have evidence of prior infection prior to Dose 1 of mRNA-1273, specifically, those in mRNA-1273 (randomized to mRNA-1273 in Part A (baseline/pre-Day 1 SARS-CoV-2 negative is required for inclusion in PP Primary Series Set), and those in Placebo-mRNA-1273 group who were SARS-CoV-2 negative at PDV/unblinding at the start of Part B.

Incidence rates will be provided over the time from Dose 1 of mRNA-1273 to receipt of booster, last study participation, or data cutoff date for efficacy. Incidence rates will also be provided by calendar quarters, as well as by the following time intervals:

- After Dose 1
 - After Dose 1 of mRNA-1273
 - After Dose 1 to before Dose 2 of mRNA-1273
 - After Dose 2 of mRNA-1273
 - Dose 2 to <14 days after Dose 2
 - ≥ 14 days after Dose 2

The last time interval “ ≥ 14 days after Dose 2” of mRNA-1273 may be further partitioned into shorter intervals. For each interval, person-time is calculated for participants at risk at

the beginning of the interval, as the time from the date of the beginning of the time interval to the date of the event/censoring for subjects with an event/censor if the event/censor occurs in the interval; or the time of the interval for subjects who continue to be at risk at the end of the interval. Incidence rate, and 95% CI for incidence rate will be calculated using the exact method adjusting for person-time will be provided by treatment cohort. Number and incidence rates of COVID-19 starting 14 days after Dose 2 of mRNA-1273 will also be provided by calendar quarters.

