5.3.2.2. Analysis of Other Efficacy Endpoints

Similar analysis methods as for the endpoint of COVID-19 cases (Section 5.3.1) will be applied to the following efficacy endpoints for analysis of primary series based on the PP set, and for Part C based on the Part C PP Set, unless otherwise specified. Start date to define cases will be similar with that for the endpoint of COVID-19 cases.

- Severe COVID-19
- SARS-CoV-2 infection or COVID-19 regardless of symptomatology or severity
- Asymptomatic SARS-CoV-2 Infection
- COVID-19 using a secondary definition of symptoms
- Death caused by COVID-19

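### Part B/C SAP 5.3.2 and 5.3.2.2 put the other primary-series endpoints on the Part A PP Set, although 4.6 reserves the PP Primary Series Set for primary-series effectiveness and 5.3.1.2.1 uses it for COVID-19

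*SAP*

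**What the plan says.** Section 4 of the Part B/C SAP keeps two lists of sets apart. The Per-Protocol Set is in the list introduced by "The following analysis sets have been defined in SAP Version 2.0", so it is the Part A set. The PP Primary Series Set is new and is listed separately for the primary series.

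Section 4.6 gives its purpose: "PP Primary Series Set will be used for the effectiveness analysis of the mRNA-1273 primary series". No endpoint is excepted, and 3.3 lists severe COVID-19, infection, secondary-definition COVID-19, COVID-19 death and asymptomatic infection among the endpoints for primary-series effectiveness.

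For COVID-19, 5.3.1.2.1 follows 4.6. Its description of the early and recent cohorts ends "recent vaccinated) using the PP Primary Series Set", and the crossovers at risk are "those in Placebo-mRNA-1273 group who were SARS-CoV-2 negative at PDV/unblinding at the start of Part B".

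For the other endpoints, 5.3.2 says "for the primary series using PP Set with appropriate analysis period". Section 5.3.2.2 says that similar methods to those for COVID-19 apply "for analysis of primary series based on the PP set". Neither section gives a reason for the different set or restates an at-risk rule.

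**The concern.** The Part A PP Set was built to compare randomised arms. For a participant randomised to placebo, its dosing rule ("Participants who did not receive the second injection of IP within [21, 42] days after the first injection date will be excluded", Part A SAP 5.4) refers to placebo injections, and its infection rule refers to Day 1 of Part A. It does not describe how the open-label series was given, or whether the participant was infected before it. The PP Primary Series Set adds those conditions.

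If a programmer follows 5.3.2 literally, severe-disease, infection and death rates in the Placebo-mRNA-1273 cohort have a different denominator from the COVID-19 rates beside them. The mRNA-1273 cohort is essentially unaffected, because its members met the dosing and status conditions to enter the PP Set. Any difference therefore falls on one side of a recent-versus-early comparison.

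**Working it through.** The plan states no figure on this point and gives no count for the difference between the sets, so the check compares definitions.

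**Step 1: who is in the PP Set but not in the PP Primary Series Set, and which other rule removes them.**

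- Placebo participants who never crossed over: removed by the primary-series treatment groups (5.1.4, and Table 1 in 5.1.5).
- Crossovers with only one open-label dose: removed by the note in 5.1.4 limiting primary-series effectiveness analyses to recipients of two doses of mRNA-1273.
- Crossovers whose second open-label dose fell outside 21 to 42 days: not removed. Protocol Table 21 sets the OL-D29 visit 28 days after OL-D1 with a window of -3/+14, so on-window dosing runs from 28 - 3 = 25 to 28 + 14 = 42 days. That lies wholly inside 21 to 42, so only people dosed outside the protocol's own window are affected.
- Crossovers with a Part B major deviation affecting critical or key data: not removed.
- Crossovers with positive or missing status at the PDV: not removed from the set. Under 5.1.3, one negative and one missing test counts as missing. A detected infection may still be dealt with by censoring (Step 2). Missing status is not, since there is no detected infection at which to censor.

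**Step 2: what each endpoint says about infection before Dose 1 of mRNA-1273.**

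| Endpoint | Rule stated for that endpoint |
|---|---|
| COVID-19 | At-risk rule (5.3.1.2.1), and censoring at infection found at scheduled visits including the PDV (5.3.1.1) |
| Secondary definition | Censoring restated (5.3.2.1.2); at-risk rule not restated |
| Severe COVID-19 | 5.3.2.1.1 resets the clock to the first mRNA-1273 injection; no at-risk or censoring rule |
| Infection regardless of symptoms | 5.3.2.1.3 requires a negative reference result for seroconversion. This limits who can become a seroconversion case, not who contributes person-time. The RT-PCR route has no such condition |
| Asymptomatic infection | 5.3.2.1.4 gives the case definition only |
| COVID-19 death | No derivation in 5.3.2.1 |

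For the last four rows, the at-risk and censoring rules arrive only through the reference in 5.3.2.2 to similar methods.

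**Step 3: what the extra participants can do to a rate.** Let *f* be their share of Placebo-mRNA-1273 person-time, *r* the event rate in the rest of the cohort, and *kr* the rate among the extra participants. The observed rate is *r*[(1 - *f*) + *kf*] = *r*[1 - *f*(1 - *k*)], so it is understated by a proportion *f*(1 - *k*).

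- If the extra participants have ordinary risk (*k* = 1), the understatement is zero.
- If they were previously infected and fully protected (*k* = 0), it equals *f*.
- If the 5.3.1.1 censoring is applied, crossovers with infection detected by the PDV contribute almost no time after Dose 1, and *f* for that group is close to zero.

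The documents give neither *f* nor *k*.

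**The case against.** Four arguments weigh against the point.

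- **The protocol names this set.** Protocol 9.5.1.3 runs long-term efficacy on the PP and mITT Sets, and its Table 11 lists these endpoints. This explains where the wording may come from. It does not settle the matter, because the Part B/C SAP says it prevails where methods differ and its own 4.6 assigns another set.
- **The term may be shorthand.** Section 5.6.2.1 writes PP Set for two-dose recipients, 5.3.1.2.3 uses a hybrid name, and the COVID-19 subgroups in 5.3.1.3 are also on the PP Set. Intent is therefore uncertain, and the mismatch is with the main COVID-19 rates rather than with every COVID-19 analysis. But 5.3.1.2.1 uses the two names for two different sets, and where it chooses the PP Set, for Part B, it adds a separate at-risk rule. Sections 5.3.2 and 5.3.2.2 add none.
- **The rules carry over.** The reference to similar methods in 5.3.2.2 may well import the at-risk rule and the censoring. If so, most of the gap closes. That reading is reasonable but unstated, and missing PDV status would be excluded only if the at-risk rule is imported as well as the censoring.
- **The residue is narrow.** This stands, as Step 1 shows.

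A reader might also infer that one-dose recipients are counted as having had the primary series. The note in 5.1.4 rules that out.

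**Conclusion.** The text is wrong as written: 5.3.2 and 5.3.2.2 conflict with 4.6 and depart from 5.3.1.2.1 without explanation. The affected participants are crossovers with an off-window second dose, a Part B major deviation, or missing or non-negative PDV status, so they fall in the Placebo-mRNA-1273 cohort. This takes the deviation screen for participants randomised to mRNA-1273 to be the same in both sets.

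The size cannot be computed from the documents and is probably small. The analyses are open-label and descriptive; no hypothesis test, alpha or Part A conclusion depends on them.

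A reader might go further and conclude that effectiveness in the recently vaccinated is materially flattered, or that severe and all-COVID-19 rates cannot be compared. The documents do not support that. It would need a count of previously infected crossovers, which is not given, and near-complete protection in them. It would also need the 5.3.1.1 censoring not to apply, although that section states it for analysis of the primary series.

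**What to change.** - In 5.3.2 and 5.3.2.2, replace PP Set with PP Primary Series Set for the primary series.
- Align 5.3.1.3, where it concerns the primary series, and 5.6.2.1.
- Add one sentence to 5.3.2.2: the at-risk rule of 5.3.1.2.1 and the censoring of 5.3.1.1 apply to every primary-series endpoint.
- If the PP Set of protocol 9.5.1.3 is also wanted, report it as a supplementary analysis with its at-risk rule stated.

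The cost is SAP wording. The PP Primary Series Set already has to be derived for COVID-19, so no new data or derivation is needed.

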5.3.2.1. Derivation of Other Efficacy Endpoint

Derivation of other select efficacy endpoints are included in Section 6.3.2.1 of SAP Version 2.0 with modifications as below.

5.3.2.1.1. Derivation of Secondary Efficacy Endpoint: Severe COVID-19

The definition of severe COVID-19 was described in SAP Version 2.0.

For primary series, the time to the first occurrence of severe COVID-19 will be calculated as:

Time to the 1st occurrence of severe COVID-19 = Date of documented severe COVID-19 – Date of first injection of mRNA-1273 +1

For Part C, the time to the first occurrence of severe COVID-19 will be calculated as:

Time to the 1st occurrence of severe COVID-19 = Date of documented severe COVID-19 – Date of booster +1

5.3.2.1.2. Derivation of a secondary definition of COVID-19

The secondary definition of COVID-19 was provided in SAP Version 2.0.

Secondary definition of COVID-19 is derived using the censoring rules for the efficacy endpoint of COVID-19 cases, i.e. subjects with early infection, as detected by positive RT-PCR at scheduled visits (including Day 29 and PDV), or positive bAb against SARS-CoV-2 nucleocapsid protein in blood samples at the scheduled visits (including months 1, 2, 7, 13, 25, PDV, OL Day 29, OL Day 57, and scheduled visits in BD phase), are censored at the time of early infection. If a participant had eligible symptom(s) within 14 days of positive RT-PCR at scheduled visits, the participant is considered to be a case for secondary definition of COVID-19.

5.3.2.1.3. Derivation of serologically confirmed SARS-CoV-2 infection or COVID-19 regardless of symptomatology or severity

SARS-CoV-2 infection or COVID-19 regardless of symptomatology or severity is detected by post-baseline positive RT-PCR results, or seroconversion at scheduled visits applicable to individual treatment cohorts:

- Post-baseline positive RT-PCR in the study, or
- Seroconversion based on bAb specific to SARS-CoV-2 nucleocapsid at scheduled visits, defined by a negative bAb N-protein (*Roche* Elecsys SARS-CoV-2 assay) at respective reference(baseline) and a positive test at post-baseline.

5.3.2.1.4. Derivation of asymptomatic SARS-CoV-2 infection

Asymptomatic SARS-CoV-2 infection is identified by absence of symptoms and infections as detected by seroconversion or positive RT-PCR at scheduled visits applicable to individual treatment cohorts for Part B, Part C, and analysis of primary series with corresponding analysis periods:

- Absent of symptoms (no COVID-19 symptom for either efficacy endpoint of COVID-19, or secondary definition of COVID-19),
- AND at least one from below:

- Post-baseline positive RT-PCR at scheduled visits, or
- Seroconversion (bAb specific to SARS-CoV-2 nucleocapsid) at scheduled visits (PDV, OL Day 29, and OL Day 57 in Part B; BD Day 1, BD Day 29, and BD Day 181 in Part C), when blood samples for immunogenicity are collected.

5.3.2.2. Analysis of Other Efficacy Endpoints

Similar analysis methods as for the endpoint of COVID-19 cases (Section 5.3.1) will be applied to the following efficacy endpoints for analysis of primary series based on the PP set, and for Part C based on the Part C PP Set, unless otherwise specified. Start date to define cases will be similar with that for the endpoint of COVID-19 cases.

- Severe COVID-19
- SARS-CoV-2 infection or COVID-19 regardless of symptomatology or severity
- Asymptomatic SARS-CoV-2 Infection
- COVID-19 using a secondary definition of symptoms
- Death caused by COVID-19

5.4. Safety Analysis

Safety will be assessed by clinical review of all relevant parameters including unsolicited AEs, SAEs, MAAEs, AEs leading to withdrawal from study vaccine and/or study participation, vital signs, and physical examination findings.

Safety analysis of Part B will be based on the Safety Set. Part C safety analyses will be based on the Part C Safety Set. Safety analysis of mRNA-1273 primary series will be based on the Primary Series Safety Set. Analysis period is defined in Section 5.1. All safety analyses will be provided by treatment cohort, unless otherwise specified.

5.4.1. Unsolicited Treatment-emergent Adverse Events

A treatment-emergent AE (TEAE) is defined as any event occurring during the study not present before exposure to the IP or any event already present that worsens after exposure

to study vaccine. Worsening of a pre-existing condition after vaccination will be reported as a new AE.

Adverse events will also be evaluated by the investigator for the coexistence of MAAE which is defined as an AE that leads to an unscheduled visit to a healthcare practitioner.

Unsolicited AEs will be coded by PT and SOC using MedDRA and summarized by vaccination group.

All summary tables (except for the overall summary of AEs) for unsolicited AEs will be presented by SOC and PT or by PT only for TEAEs with counts of subjects included. SOC will be displayed in internationally agreed order.

When summarizing the number and percentage of subjects with an event, subjects with multiple occurrences of the same AE or a continuing AE will be counted once. Only the maximum severity level will be presented in the severity summaries, and the strongest relationship level will be presented in the relationship summaries. Percentages will be based upon the number of subjects in the Safety Set within each treatment cohort.

Unsolicited TEAEs will be summarized for Part B, Part C, and Primary Series using analysis periods as defined in Section 5.1.

